5 STUDY DESIGN AND PLAN

This is a multicenter, randomized, double-blinded, placebo-controlled study to evaluate safety and preliminary efficacy of SIR1-365 in patients with severe COVID-19. The primary objective is to assess the overall safety and tolerability of SIR1-365 administered orally at 100 mg, 3 times per day (TID) for 14 days relative to the placebo group. The secondary objectives are to assess the effects of SIR1-365 on clinical efficacy endpoints and the biomarkers indicative of

inflammation, target engagement, kidney injury and CV endothelial cell damage as well as SIR1-365 pharmacokinetics (PK).

Approximately 60 eligible patients will be randomly assigned at a 1:1 ratio to receive either SIRI-365 at 100 mg, TID or matching placebo for up to 14 consecutive days. For ethical and medical reasons, standard-of-care treatments for COVID-19 will be provided to all patients. Study treatments (either SIRI-365 or matching placebo) will be given as add-on therapy.

Patients could be hospitalized and treated for up to 14 days. Patients will be assessed daily while hospitalized. If the patients are discharged from the hospital before Day 14, all the assessments planned for Day 14 should be carried out before discharge. If a patient is still hospitalized after Day 14, no study drug will be administered after the last dose on Day 14.

It is preferred that the follow-up visit is in person to obtain safety laboratory tests. However, infection control or other restrictions may limit the ability of the patients to return to the clinic. In this case, the follow-up visit may be conducted by phone and only safety data will be obtained. Study drugs will not be administered for early discharged patients. Follow-up visit will be scheduled approximately on Day 28 (± 3) or 14(± 3) days after the last dose for those who are discharged from the hospital before Day 14.

Table 5.1 Treatment Administered

Study drug name:	SIR1-365		Placebo	
Dosage formulation:	Tablets		Matching tablets	
Unit dose strength/Dosage level:	100 mg tablets		NA	
Route of administration	Oral/gastric tube		Oral/gastric tube	
Dosing instructions:	Take 1 tablet three times daily			

Food and water will be allowed as needed.

Study procedures to assess safety, preliminary efficacy, biomarkers, and PK are shown in below table.

Table 5.2 Schedule of Assessments¹²

Days	Screening	Treatment in Hospital								Follow-up Visit/EOS
	-7 to -1	1 ¹	2-6	7	8-9	10	11-13	14 (± 2) /EOT ²		
Informed consent	X									
Medical history	X									
Demographics	X									
Physical examinations	X ⁴								X	
Vital signs ⁵	X	X	X	X	X	X	X	X		X

12-lead ECG	X	X ⁶		X		X		X	X
Blood samples for routine lab tests including CRP and ferritin ⁷	X	X	X	X	X	X	X	X	X
Blood samples for coagulopathy and cardiac panels ⁸		X	X	X		X		X	X
Urine sample for urinalysis	X	X	X	X		X		X	X
Serum serology and pregnancy tests for screening	X								
Inclusion and exclusion	X								
Randomization		X							
Treatment		X	X	X	X	X	X	X	
Oxygen use and saturation (pulse oximetry)	X	X	X	X	X	X	X	X	X
PaO ₂ /FiO ₂ ratio	X	X		X				X	
WHO ordinal scale		X		X				X ¹³	X
Blood sample for cytokine/chemokine panels and CV biomarkers ⁹		X		X				X	
Blood sample for PK analysis and pRIP1/pMLKL assay ¹⁰		X		X				X	
Urine sample for NGAL and KM-1 assay ¹¹		X		X				X	
AE and ConMed	X	X	X	X	X	X	X	X	X

1. Enrollment and Baseline. Screening and Baseline visits can be combined. ECG, laboratory test and other test results taken within 24 hours prior to consent will be used as Baselines.
2. End of Treatment (EOT) or early discharge.
3. End of the study (EOS) or early discontinuation.
4. For enrolled patients, physical examination obtained at screening will be the Baseline. Weight and height will be measured at screening.
5. Vital signs will be taken before the 1st dose on Day 1 as Baseline, and within 3 hours before the 2nd dose on other days.
6. Three ECGs with 1-3 min interval before the 1st dose on Day 1 only, and the means of the 3 ECGs will be used as Baselines. ECGs will be done within 3 hours before the 2nd dose on other days. Local ECG machine will be used in this study.
7. Routine laboratory tests before the 2nd dose will be done daily at local labs. CRP and ferritin tests will be done on Days 1, 3, 7, 10 and 14.
8. Coagulopathy panel including D-dimer, fibrinogen, PT, PTT and INR, and cardiac function panel including NT-proBNP (or BNP) and high-sensitivity cardiac troponin will be done on Days 1, 3, 7, 10 and 14 at local labs with samples collected before the 2nd dose.
9. One blood sample collected before the 1st dose on Day 1 and before the 2nd dose on Days 7 and 14 for cytokine/chemokine panels and CV biomarker assays to be conducted at a central lab

10. One blood sample will be collected from each patient within 30 min before and 2 hours (± 5 min) after the 1st dose on Day 1, respectively. On Days 7 and 14, one blood sample will be collected within 30 min before and 2 hours (± 5 min) after the 2nd dose, respectively. Each plasma sample will be divided into 4 parts, 2 for PK analysis and 2 for plasma pRIP1/pMLKL assay conducted at a central lab. PBMC preparation will be done at the sites with necessary equipment according to the laboratory manual for pRIP1/pMLKL assay.
11. About 10 mL of urine sample will be collected before dosing on Day 1, and in the morning on Days 7 and 14 for NGAL and KIM-1 assay to be conducted at a central lab
12. If the patients are discharged from the hospital before Day 14, all the assessments planned for Day 14 should be carried out before discharge. Study drugs will not be administered in early discharged patients. It is preferred that the follow-up visit is in person to obtain safety laboratory tests. However, infection control or other restrictions may limit the ability of the patients to return to the clinic. In this case, the follow-up visit may be conducted by phone and only safety data will be obtained. If a patient is still hospitalized after Day 14, no study drug will be administered after the last dose on Day 14.
13. When completing the WHO Ordinal Scale at Day 14/ EOT, if the subject has received physician orders to be discharged from the hospital, the score should be a 3 or less (*no longer hospitalized*).

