#### **8.3.1. Inflammatory Biomarkers**

##### **8.3.1.1. [REDACTED]**

As a proinflammatory biomarker [REDACTED] significantly elevated in COVID-19 patients and is associated with disease severity and progression. Thus [REDACTED] a reliable indicator of hyperinflammatory state.

[REDACTED] will be measured daily at local laboratories with validated methods. Change from baseline to Day 7, time (days) and number of the patients to reach 50% reduction from Baseline in [REDACTED] during the treatment period (Baseline to Day 14), and changes in daily plasma [REDACTED] during the treatment period (Baseline to Days 1-14) will be analyzed.

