6 DETERMINATION OF SAMPLE SIZE

Due to the exploratory nature of this study, the sample size is not calculated based on statistical significance on any parameters. However, a sample size of 30 patients per group is considered to be sufficient to detect marked differences in the overall safety profile between treatments with a pre-specified safety monitoring plan. Furthermore, this sample size provides estimates of treatment differences in some clinical efficacy endpoints and the levels of some biomarkers such as CRP, for use in planning future studies. Therefore, approximately 30 patients will be enrolled for each group (total 60) in this study.

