8 GENERAL ANALYSIS CONSIDERATIONS

The statistical analyses will be reported using summary tables, listings, and figures (TLFs). The International Council for Harmonisation (ICH) numbering convention will be used for all TLFs.

Unless otherwise noted, all statistical testing will be 2-sided and will be performed at the 0.05 significance level. Tests will be declared statistically significant if the calculated P-value is <0.05 .

Continuous variables will be summarized by presenting the number of observations, mean, standard deviation, median, minimum, and maximum. Other summaries (eg, 95% confidence interval [CI]) may be used as appropriate.

Categorical variables will be summarized by presenting counts and percentages of patients in corresponding categories. All possible categories as defined in the CRF should be populated, even

if they have zero counts. Percentages for missing values are omitted and do not account for the percent calculation of other categories. Percentages are based on the total category count excluding the missing category if not otherwise mentioned. In certain tables (eg, AEs), the total number of patients in the analysis set is used as denominator. Footnotes in the table will specify the percent basis in those cases.

All summary tables will be presented by treatment group and a total column (except efficacy tables). Baseline summaries will also include a total summary column.

Individual patient data obtained from the eCRFs, external vendors (eg, laboratory data, ECG data), PK data, and any derived data will be presented by patient in data listings.

The analyses described in this plan are considered a priori, in that they have been defined before breaking the blind.

Any analyses performed after breaking the blind which are not specified in this analysis plan (or subsequent version prior to unblinding) will be considered post hoc and exploratory. Post hoc analyses will be labeled as such on the output and identified in the CSR.

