All analyses and tabulations will be performed using SAS software Version 9.4 or higher. TLFs will be presented in rich text format (RTF). Additionally, collated portable document format (PDF) of all tables, listings and figures will be provided. Upon completion, all SAS programs and outputs will be validated by an independent programmer. In addition, all program output will undergo a senior level statistical review. The validation process will be used to confirm that statistically valid methods have been implemented and that all data manipulations and calculations are accurate. Checks will be made to ensure accuracy, consistency with this plan, consistency within tables, and consistency between tables and corresponding data listings. Upon completion of validation and quality review procedures, all documentation will be collected and filed by the project statistician or designee.

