As a sensitivity analysis, to assess the impact of missing data, if more than 10% of patients in either arm has missing Day 7 CRP values, a MMRM analysis will be performed. The plasma CRP levels will be analyzed by a MMRM with treatment group, Day (Days 2 to 14), and treatment group-by-Day interaction as fixed factors, and the Baseline score as a continuous covariate. Day will be used as the repeated measure using an unstructured covariance structure. For both treatment groups, at Day 7, the geometric LS mean in plasma CRP levels and corresponding 95% CI will be presented. The output will also include the estimated geometric LS mean ratio for SIR1-365 dose and placebo, the corresponding 95% CI and corresponding two-sided P-value for the ratio.

Additionally, the primary analysis for plasma CRP level on Day 7 and Day 14 will be repeated for PP set with no missing data imputation.

A separate summary table will be produced, similar to what is described above, summarizing the results at Day 7 (assessments taking place on study day 7) and Day 14 (assessments taking place on study day 14). For any patients with missing Day 7 results, the Day 7 results will be imputed using the last value reported prior to study day 7. Similarly, Day 14 missing observations will be imputed with the last available assessment that took place after study day 7 and prior to study day 14. A summary table will be produced on the PP set, summarizing these (imputed and reported) results.

Time to 50% reduction:

Time (days) to 50% reduction from Baseline in plasma CRP level during the treatment period will be analyzed using a Cox proportional hazards model to estimate the hazard ratio and corresponding 95% CI for SIR1-365 dose vs placebo.

The proportional hazard regression model will include treatment as a fixed effect.

- Patients without a 50% reduction will be censored at the date of their last CRP assessment.
- Patients with no post-baseline CRP value will be censored at Day 1.
- Death, prior to 50% reduction, will be handled as a competing risk event.

The hazard ratio estimation of the event of interest will be derived from a cumulative incidence function. The number and percentage of patients to reach 50% reduction from Baseline in plasma CRP level from Baseline to Day 14 will also be summarized. This analysis will be performed in the ITT set.

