14.1.2.1 Time to first time back to normal

Time to first time back to normal (in days) is the number of days between the date of first study drug administration and the first date that the result of the parameter of interest returns back to within a normal range. Parameters used for this analysis will be ferritin, lymphocytes and neutrophils.

Time to first time back to normal will be analyzed using a Cox proportional hazards model to estimate the hazard ratio and corresponding 95% CI for SIR1-365 dose vs placebo.

The proportional hazard regression model will include a single term for treatment.

- Patients with a baseline value falling within the normal range will be censored on the first date of study drug administration.
- Death prior to returning back to normal will be handled as a competing risk event.
- Patients that do not return back to normal over the assessment period will be censored at the date of last assessment
- Patients with no post-baseline assessment value will be censored at Day 1.

The hazard ratio estimation of the event of interest (first time back to normal) will be derived from a cumulative incidence function. The Kaplan Meier estimate of median time to event will also be presented for each treatment group.

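### Time to 50% CRP reduction is fitted by a continuous-time Cox model to samples on Days 3, 7, 10 and 14 with no rule for ties, intervals or discharge dates, so the hazard ratio depends on an unrecorded software option

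*SAP*

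**What the plan says.** SAP 5 (Table 5.2, footnote 7) states that "CRP and ferritin tests will be done on Days 1, 3, 7, 10 and 14", and SAP 14.1.1 repeats those days for CRP. For early discharge, the Day 14 assessments are brought forward. SAP 8.4 then reports them under Day 14/EOT.

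SAP 14.1.1 states: "Time (days) to 50% reduction from Baseline in plasma CRP level during the treatment period will be analyzed using a Cox proportional hazards model". The model has a single treatment term. Patients who do not halve are censored at their last CRP date, death is a competing event, and the hazard ratio is taken from a cumulative incidence function. The analysis set is ITT.

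On software, SAP 8 says only "All analyses and tabulations will be performed using SAS software Version 9.4 or higher". No procedure, tie method, interval-censoring method or grouped-time method is named. Nor does the SAP say whether a halving first seen at discharge is dated at discharge or at Day 14.

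SAP 14.1.2.1 uses the same model for ferritin and white cell counts: "Time to first time back to normal will be analyzed using a Cox proportional hazards model". SAP 11.7.1 does so for coagulation parameters.

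Protocol 8.3.1.1 says the marker "will be measured daily at local laboratories with validated methods". Its name is redacted there, but the table of contents lists the section as CRP levels. This conflicts with the five-day schedule.

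**The concern.** A continuous-time Cox model assumes that event times are close to exact. Here every halving is pushed to the next sample, so many patients share a few event times. The partial likelihood must then be approximated or replaced, and the available methods do not estimate the same quantity when ties are this heavy.

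The SAP presents its analyses as fixed before unblinding, and its sample-size section gives estimation of biomarker differences, CRP among them, as one purpose of the trial. A hazard ratio that shifts with an unrecorded programming choice does not serve that purpose. This is also the CRP analysis assigned to the full ITT set.

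**Working it through.** **No plan figure to reproduce.** The SAP says "the sample size is not calculated based on statistical significance on any parameters" and gives no hazard ratio, event count or power for this endpoint.

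**Inputs from the documents.** "approximately 30 patients will be enrolled for each group (total 60) in this study"; 1:1 allocation; "all statistical testing will be 2-sided and will be performed at the 0.05 significance level"; post-baseline CRP on Days 3, 7, 10 and 14 plus discharge. The gaps between samples are 3−1 = 2, 7−3 = 4, 10−7 = 3 and 14−10 = 4 days.

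**Assumptions, not in the documents.** Exponential time to halving; placebo median 3, 5 or 8 days; true HR 1.0, 1.5 or 2.0; no deaths unless stated; discharge independent of CRP.

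**Orientation.** Power = Φ(√(events/4) × ln HR − 1.96). With 60 events and HR 2.0: Φ(3.873 × 0.693 − 1.96) = Φ(0.72) = 77%. With 45 events: 64%.

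**Why the tie method matters: one sampling day by hand.** Take placebo median 3 days, HR 2.0 and the Day 3 sample, 2 days after baseline.
- Placebo: p0 = 1 − 2^(−2/3) = 0.370. Active: p1 = 1 − (2^(−2/3))² = 0.603.
- Breslow with a single tied time solves to the risk ratio: 0.603/0.370 = 1.63.
- The discrete method targets the odds ratio: (0.603/0.397)/(0.370/0.630) = 2.59.
- The complementary log-log (grouped-time) model targets ln(1−p1)/ln(1−p0) = 2.00.

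The same data thus give answers on both sides of the truth.

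**Main simulation.** 600 trials per row, 30 per arm, true HR 2.0. Cells show the geometric mean HR, with power in brackets.

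| Placebo median; discharge | Tied | Exact times | Breslow | Efron | Discrete | Grouped-time |
|---|---|---|---|---|---|---|
| 3 d; none early | 99.6% | 2.02 (73.8%) | 1.52 (24.3%) | 1.87 (65.3%) | 2.83 (67.2%) | 2.07 (70.5%) |
| 3 d; median Day 8 | 95.5% | 2.00 (64.8%) | 1.55 (24.3%) | 1.84 (56.3%) | 2.52 (57.5%) | not run |
| 5 d; none early | 100% | 2.07 (73.5%) | 1.69 (43.7%) | 2.00 (70.8%) | 2.66 (72.3%) | 2.12 (74.0%) |
| 5 d; median Day 8 | 94.2% | 2.00 (57.8%) | 1.69 (35.8%) | 1.94 (55.5%) | 2.37 (54.7%) | not run |
| 8 d; none early | 100% | 2.03 (68.0%) | 1.78 (47.2%) | 2.00 (65.0%) | 2.36 (66.2%) | 2.05 (68.2%) |
| 8 d; median Day 8 | 92.4% | 2.07 (52.5%) | 1.83 (37.0%) | 2.03 (49.2%) | 2.30 (50.0%) | not run |

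- **True HR 1.5:** Breslow 1.30–1.43, Efron 1.44–1.53, discrete 1.61–1.84, grouped-time 1.51–1.55.
- **True HR 1.0:** all methods estimate 0.98–1.01. Rejection rates are Breslow 0.3–2.8%, Efron 3.5–7.2%, grouped-time 4.8–8.3% and exact times 3.7–7.0%. The simulation standard error at 5% is √(0.05 × 0.95/600) = 0.9 points.

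**Further checks, true HR 2.0.**
- 1,500 trials, placebo median 3 or 5 days, discharge uniform over 3–20 days: Breslow 1.54–1.68 (power 23–36%), Efron 1.87–1.94 (about 60%), grouped-time 2.05–2.07 (65–68%). Type I error: 0.5–1.9%, 4.8–4.9% and 5.3–6.2%.
- 500 trials, with and without 10% deaths: Breslow 1.54–1.78 (27–41%), Efron 1.82–1.97 (54–64%), grouped-time 1.95–2.09 (55–68%).
- Day 7 and Day 10 visits moved by 1 day and Day 14 by 2 days: 93–95% still tied; Breslow 1.63–1.75 (34–46%).
- Daily testing, placebo median 5 days: 95–96% tied, but Breslow gives 1.88–1.92.

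**The case against.** A reader might infer that the plan as written pulls the hazard ratio towards 1, loses most of the power and could report a real anti-inflammatory effect as absent. The documents do not support that.

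- **Direction.** It follows from the tie option, and none is stated. That the SAS procedure would default to Breslow is an assumption about software. Efron shows at most about 8% attenuation (1.84/2.0 = 0.92), and the discrete option moves away from 1.
- **Power.** Even under Breslow, the loss ranges from severe (73.8% to 24.3%) to moderate (52.5% to 37.0%).
- **Other analyses.** SAP 14.1.1 also has ANCOVA on log CRP at Days 7 and 14, Wilcoxon tests, a conditional MMRM, the proportion reaching 50% reduction and Kaplan-Meier curves. Cox ties affect none of these.
- **Status.** This is an unpowered secondary endpoint in an exploratory Phase 1b study. Its p-values are only an aid to interpretation.

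All of this stands and limits the consequence. The percentage tied does not by itself measure harm either: daily testing gives similar ties with little bias. Nor is the schedule perfectly rigid, since Day 14 has a ±2-day window and unscheduled tests may occur, but moving the visits left the result much the same.

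Two limits of the check also stand. Discharge was simulated as unrelated to CRP, and the ferritin and coagulation endpoints were not simulated. Finally, Efron removes most of the attenuation, so preferring the grouped-time model over it is partly a matter of judgement.

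None of this supplies the missing rule.

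**Conclusion.** The point holds as an unspecified analysis choice with a material effect. On the SAP schedule over 90% of event times are tied, and one true hazard ratio of 2.0 can be reported as anything from about 1.5 to 2.8 depending on an option the SAP leaves open. Material attenuation, low power and a type I error well below 5% arise only under Breslow ties.

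The figures rest on exponential times, a placebo median of 3 to 8 days and discharge independent of CRP. A 10% death rate did not change the picture. If CRP were in fact measured daily, as Protocol 8.3.1.1 says, the Breslow bias would be small. What is affected is the interpretation of secondary biomarker endpoints and the planning of later studies. The primary safety conclusion is untouched.

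**What to change.** In SAP 14.1.1:
- Treat halving as lying between the last CRP above 50% of Baseline and the first at or below it.
- Estimate the hazard ratio with a grouped-time proportional hazards model (complementary log-log link; intervals Days 2–3, 4–7, 8–10 and 11–14) or an interval-censored proportional hazards model. At the least, name Efron ties.
- Date a discharge CRP at its actual study day and place it in the interval where that day falls.
- Keep patients who die before halving event-free to Day 14, in line with the planned cumulative-incidence approach. If Efron ties are chosen instead, confirm that the option is available for the competing-risk fit.

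Apply the same rule to ferritin (14.1.2.1) and to the coagulation panel sampled on the same five days (11.7.1). White cell and platelet counts come from the daily routine tests, so their intervals would be daily. Reconcile Protocol 8.3.1.1 with the five sampling days in the SAP.

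The cost is SAP wording and a few lines of code, with no new data. There are two small downsides. The order of events within an interval is ignored, and the grouped-time test may be slightly liberal at 30 per arm. It rejected 5.3–6.2% in the 1,500-trial runs; the 8.3% in one 600-trial run came where exact times also gave 7.0%.

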### ***Laboratory Analyses***

Laboratory data including coagulopathy panel and cardiac function panel will be summarized using summary statistics of raw data and change from Baseline values (pre-dose Day 1 values/last non-missing pre-dose value), by presenting shift tables using clinically notable ranges (Baseline to most extreme postbaseline value), and by flagging notable values in data listings. The number and percentage of patients with clinically meaningful laboratory test findings will also be summarized by treatment group and visit.

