8.2 Standard Calculations

Variables requiring calculations will be derived using the following formulas:

- Baseline: A Baseline value, unless specified otherwise, is the last non-missing value recorded prior to the first dose of study drug.
- Study day: For a given date, study day will be calculated as the number of days from the day of first dosing of study drug, labeled day 1, therefore:

Study day = date of event/measurement - date of first dose of study drug + 1, for events/measurements on or after first dose

Study day = date of event/measurement - date of first dose of study drug, for events/measurements before first dose

- Durations (days): Durations, expressed in days, will be calculated as follows:

Duration in days = (Stop date/time of event – Start date/time of event)/(3660x24)

If the stop or start time is missing, only the date information will be used as follows:

Duration in days = Stop date of event – Start date of event + 1

- Height: Height entries made in inches are converted to centimeters using the following formula:

Height (cm) = Height (in) × 2.54

- Weight: Weight entries made in pounds are converted to kilograms using the following formula:

Weight (kg) = Weight (lb)/2.2046

- Body Mass Index (BMI): BMI is calculated using height and weight and is calculated using the following formula:

BMI (kg/m²) = Weight (kg) / [[Height (cm) / 100]²]

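### Day 1 timing of routine labs and the coagulation and cardiac panels does not secure a pre-dose baseline, and the two panels have no scheduled Screening sample to fall back on

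*SAP*

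**What the plan says.** **Collection.** In SAP Table 5.2, footnote 8 states that the coagulation and cardiac panels "will be done on Days 1, 3, 7, 10 and 14 at local labs with samples collected before the 2nd dose". Footnote 7 reads "Routine laboratory tests before the 2nd dose will be done daily at local labs". Footnotes 7 and 8 of the protocol Schedule of Assessments give the same timing. Other footnotes separate Day 1 from later days; for example, footnote 5 says "Vital signs will be taken before the 1st dose on Day 1 as Baseline, and within 3 hours before the 2nd dose on other days".

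**Where samples are scheduled.** The row "Blood samples for routine lab tests including CRP and ferritin" is marked at Screening and on Day 1. The row "Blood samples for coagulopathy and cardiac panels" is blank at Screening, so its first mark is Day 1.

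**Analysis.** SAP 8.2 says a baseline value, unless specified otherwise, "is the last non-missing value recorded prior to the first dose of study drug". Protocol 10.3 gives the same general rule. Protocol 10.3.2 (Laboratory Analyses) names both panels and defines their baseline as "pre-dose Day 1 values/last non-missing pre-dose value".

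**Other source of a baseline.** Footnote 1 of both schedules accepts laboratory results from the 24 hours before consent as baseline.

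**The concern.** The analysis needs a value taken before the first dose, but the collection rule for these tests is tied to the second dose on every day, Day 1 included. A site can follow the schedule exactly and still produce a Day 1 sample that the SAP cannot use as baseline.

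For the two panels no other sample is scheduled before dosing. At stake are the secondary safety measures on coagulopathy and cardiac function (SAP 4) and two analyses that depend on the same baseline:

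- the Wilcoxon comparison of percentage change in D-dimer (SAP 11.7);
- the time-to-normal Cox model for coagulation parameters (SAP 11.7.1), which censors patients whose baseline is normal and gives no rule for a missing baseline.

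The carry-forward rules in SAP 11.7 and 11.8 fill Days 7, 14 and 28 only; they do not fill baseline.

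**Working it through.** The plan states no figure for this point, so the check compares passages and adds a short timing calculation.

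**Step 1. Day 1 timing by footnote (same numbering in both schedules).**

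| Assessment | Footnote | Day 1 timing | Screening sample |
|---|---|---|---|
| Vital signs | 5 | before 1st dose | yes |
| ECG | 6 | before 1st dose | yes |
| Routine labs, with CRP, ferritin, platelets | 7 | before 2nd dose | yes |
| Coagulation and cardiac panels | 8 | before 2nd dose | none |
| Cytokines, chemokines, CV biomarkers | 9 | before 1st dose | none |
| Drug level and pRIP1/pMLKL | 10 | before and 2 h after 1st dose | none |
| Urine NGAL and KIM-1 | 11 | before dosing | none |

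Only footnotes 7 and 8 leave out a pre-dose Day 1 clause. Only the row under footnote 8 lacks both that clause and a Screening sample. The Day 1 visit list (protocol 9.2) gives the two panels no timing. The protocol's list of changes for V2.2 records that some assessments moved from before the first dose to before the second, which may explain the omission.

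**Step 2. How late a compliant Day 1 sample can be.** Protocol 6.1 sets dosing every 8 hours ± 1 hour from the first dose. The second dose is therefore due 8 − 1 = 7 to 8 + 1 = 9 hours after the first, and a sample drawn just before it falls at about 7 to 9 hours. When Screening and baseline are combined, Day 1 may have fewer than three doses (protocol 3.1). If only one is given that day, the footnote defines no Day 1 draw time.

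**Step 3. Is the patient exposed by then?** Protocol 2.4 gives a peak at 1–2 hours and a half-life of 6–7 hours in healthy volunteers. Assuming mono-exponential decline after the peak (my assumption, for illustration), the fraction of peak remaining is 2^(−(t − tmax)/t½):

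- t = 7 h: 2^(−6/6) = 0.50 to 2^(−5/7) = 0.61
- t = 8 h: 2^(−7/6) = 0.45 to 2^(−6/7) = 0.55
- t = 9 h: 2^(−8/6) = 0.40 to 2^(−7/7) = 0.50

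Such a sample follows the peak, with roughly 40–61% of it remaining.

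**Step 4. What baseline is left if the Day 1 sample is late.**

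- Routine labs, CRP, ferritin, platelets: the last pre-dose value is the Screening value, at most 7 days old (SAP Table 5.2, Days −7 to −1).
- Coagulation: D-dimer, fibrinogen, PT, PTT and INR have no scheduled pre-dose value. SAP 11.7 lists six parameters; platelet count is the sixth, so five of six lose baseline.
- Cardiac: NT-proBNP/BNP and troponin, the whole panel, have no scheduled pre-dose value.
- The one rescue is footnote 1, and no section requires either panel in the 24 hours before consent.

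**Step 5. Size per patient.** With about 30 patients per arm, each missing baseline removes 1/30 = 3.3% of an arm from the change-from-baseline summaries. The documents give no basis for estimating how many patients this would be.

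**The case against.** The strongest reply is that this is an ambiguity and not a conflict. A sample drawn before the first dose is also before the second, so one draw can satisfy both the footnotes and the baseline rule. The intent is visible: Day 1 is labelled baseline in the schedule and in protocol 9.2, protocol 8.2 takes safety baselines from pre-dose values, and protocol 10.3.2 asks for a pre-dose Day 1 value for these panels. The overnight fast in protocol 8.2.4 points to a morning draw, though the first dose is not tied to a clock time. All of this stands. It shows what was meant, but it does not secure the sample.

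Four stronger readings are tempting, and the documents do not support them:

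- *The footnotes contradict the baseline definition.* They permit a late draw; they do not require one.
- *Every patient at a site following the footnotes loses baseline.* That assumes the latest permitted draw each time and no usual-care result.
- *No pre-dose panel value can exist, so both endpoints lose baseline entirely.* Footnote 1 allows a value from before consent, and platelets keep a Screening value.
- *Change will be measured from a drug-exposed value.* SAP 8.2 already excludes such a value. It would enter only if programming mapped Day 1 to baseline by visit label. Nor do the documents show that one dose shifts these parameters within 9 hours.

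It is also fair that the primary endpoint (TEAEs) is untouched, that most of these summaries are descriptive, and that observed values by visit remain available.

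**Conclusion.** The concern holds as a gap between collection and analysis. Footnotes 7 and 8 allow a Day 1 draw about 7 to 9 hours after the first dose, and the analysis rules do not accept that value as baseline. For a patient drawn late with no usual-care panel from the 24 hours before consent, change from baseline is missing for five coagulation parameters and both cardiac markers. For routine labs, CRP and ferritin the effect is milder: an older but valid Screening baseline, as the SAP's own rule provides. CRP is an inclusion criterion, so its Screening value should exist for every eligible patient.

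The conclusion rests on the schedule text, the 8 ± 1 hour interval and the blank Screening cell for the panels. It does not depend on the illustrative drug-level calculation. The number of patients affected is unknown and could be zero if sites draw before dosing by habit. The point is worth correcting because the remedy is specific and cheap.

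**What to change.** 1. In the protocol Schedule of Assessments, amend footnotes 7 and 8 so that the Day 1 sample is taken before the first dose and samples on other days before the second, as footnotes 5, 6 and 9 already do. Mirror this in SAP Table 5.2. The protocol change governs when blood is drawn; the SAP table only repeats it.
2. In the SAP, state that Day 1 panel values timed after the first dose are not mapped to baseline by visit label. This applies SAP 8.2 explicitly and needs the clock time of local-laboratory draws. The protocol states that clock time is recorded for drug-level samples (8.4); confirm that the eCRF captures it for local laboratories.
3. Report, by arm, how many patients lack a pre-dose value for each panel, and say how SAP 11.7.1 treats them.

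Cost: four footnotes across two documents, a small protocol amendment with IRB approval (protocol 13), and a few lines in the SAP. No extra sample is needed. Steps 2 and 3 remain useful if sampling is already complete.
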